15.3 DERIVED VARIABLES

Analyses visits will be derived per Section 15.2. Observed data will be used for the primary and secondary objectives without derivation.

15.4 REPEATED OR UNSCHEDULED ASSESSMENTS OF SAFETY PARAMETERS

If a patient has repeated assessments before the start of the first treatment, the results from the final non-missing assessment made prior to the start of the study treatment will be used as baseline. If end-of-study assessments are repeated or if unscheduled visits occur, the last non-missing Post-treatment assessment will be used as the end-of-study assessment for generating summary statistics. However, all Post-treatment assessments will be used for PCS value determinations, and all assessments will be presented in the data listings.

15.5 MISSING DATE OF THE LAST DOSE OF STUDY TREATMENT

When the date of the last dose of study treatment is missing for a patient in the Safety Population, all efforts should be made to obtain the date from the Investigator. If after all efforts are made it is still missing, the last available dosing record date will be used as the last dose date.

15.6 MISSING SEVERITY ASSESSMENT FOR ADVERSE EVENTS

If severity is missing for an AE that started before the date of the first dose of study treatment, an intensity of mild will be assigned. If severity is missing for an AE that started on or after the date of the first dose of study treatment, an intensity of severe will be assigned. The imputed values for severity assessment will be used for the incidence summary; the values will be shown as missing in the data listings.

15.7 MISSING CAUSAL RELATIONSHIP TO STUDY DRUG FOR ADVERSE EVENTS

If the causal relationship to the study treatment is missing for an AE that started on or after the date of the first dose of study treatment, a causality of yes will be assigned. The imputed values for causal relationship to study treatment will be used for the incidence summary; the values will be shown as missing in the data listings.

15.8 MISSING DATE INFORMATION FOR ADVERSE EVENTS

The following imputation rules only apply to cases in which the start date for AEs is incomplete (i.e., partly missing).

Missing month and day

- If the year of the incomplete start date is the same as the year of the first dose of study treatment, the month and day of the first dose of study treatment will be assigned to the missing fields
- If the year of the incomplete start date is before the year of the first dose of study treatment, *December 31* will be assigned to the missing fields
- If the year of the incomplete start date is after the year of the first dose of study treatment, *January 1* will be assigned to the missing fields

Missing month only

- If only the month is missing, the day will be treated as missing and both the month and the day will be replaced according to the above procedure

Missing day only

- If the month and year of the incomplete start date are the same as the month and year of the first dose of study treatment, the day of the first dose of study treatment will be assigned to the missing day

- If either the year of the incomplete start date is before the year of the date of the first dose of study treatment or if both years are the same, but the month of the incomplete start date is before the month of the date of the first dose of study treatment, the last day of the month will be assigned to the missing day
- If either the year of the incomplete start date is after the year of the date of the first dose of study treatment or if both years are the same, but the month of the incomplete start date is after the month of the date of the first dose of study treatment, the first day of the month will be assigned to the missing day

If the stop date is complete and the imputed start date as above is after the stop date, the start date will be imputed by the stop date.

If the start date is completely missing and the stop date is complete, the following algorithm will be used to impute the start date:

- If the stop date is after the date of the first dose of study treatment, the date of the first dose of study treatment will be assigned to the missing start date
- If the stop date is before the date of the first dose of study treatment, the stop date will be assigned to the missing start date

15.9 MISSING DATE INFORMATION FOR PRIOR OR CONCOMITANT MEDICATIONS

For prior or concomitant medications, incomplete (i.e. partly missing) start dates and/or stop dates will be imputed. When the start date and the stop date are both incomplete for a patient, the start date will be imputed first.

15.9.1 Incomplete Start Date

The following rules will be applied to impute the missing numeric fields for an incomplete prior or concomitant medication start date. If the stop date is complete (or imputed) and the imputed start date is after the stop date, the start date will be imputed using the stop date.

Missing month and day

- If the year of the incomplete start date is the same as the year of the first dose of study treatment, the month and day of the first dose of study treatment will be assigned to the missing fields
- If the year of the incomplete start date is before the year of the first dose of study treatment, *December 31* will be assigned to the missing fields

- If the year of the incomplete start date is after the year of the first dose of study treatment, *January 1* will be assigned to the missing fields

Missing month only

- If only the month is missing, the day will be treated as missing and both the month and the day will be replaced according to the above procedure

Missing day only

- If the month and year of the incomplete start date are the same as the month and year of the first dose of study treatment, the day of the first dose of study treatment will be assigned to the missing day
- If either the year of the incomplete start date is before the year of the date of the first dose of study treatment or if both years are the same, but the month of the incomplete start date is before the month of the date of the first dose of study treatment, the last day of the month will be assigned to the missing day.
- If either the year of the incomplete start date is after the year of the date of the first dose of study treatment or if both years are the same, but the month of the incomplete start date is after the month of the date of the first dose of study treatment, the first day of the month will be assigned to the missing day

15.9.2 Incomplete Stop Date

The following rules will be applied to impute the missing numeric fields for an incomplete prior or concomitant medication stop date. If the date of the last dose of study treatment is missing, impute it as described in Section 15.4. If the imputed stop date is before the start date (imputed or non-imputed start date), the imputed stop date will be equal to the start date.

Missing month and day

- If the year of the incomplete stop date is the same as the year of the last dose of study treatment, the month and day of the last dose of study treatment will be assigned to the missing fields
- If the year of the incomplete stop date is before the year of the last dose of study treatment, *December 31* will be assigned to the missing fields
- If the year of the incomplete stop date is after the year of the last dose of study treatment, *January 1* will be assigned to the missing fields

Missing month only

- If only the month is missing, the day will be treated as missing and both the month and the day will be replaced according to the above procedure

Missing day only

- If the month and year of the incomplete stop date are the same as the month and year of the last dose of study treatment, the day of the last dose of study treatment will be assigned to the missing day
- If either the year of the incomplete stop date is before the year of the date of the last dose of study treatment or if both years are the same but the month of the incomplete stop date is before the month of the date of the last dose of study treatment, the last day of the month will be assigned to the missing day
- If either the year of the incomplete stop date is after the year of the date of the last dose of study treatment or if both years are the same but the month of the incomplete stop date is after the month of the date of the last dose of study treatment, the first day of the month will be assigned to the missing day

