8.0 DEMOGRAPHICS AND OTHER BASELINE CHARACTERISTICS

Demographic parameters (age; age group; race; ethnicity; sex), baseline characteristics (weight; height; and body mass index, calculated as weight [kg]/(height [m])²) will be summarized descriptively by treatment group separately for each phase.

The number and percentage of patients with medical histories in each system organ class and preferred term will be summarized by treatment group separately for each phase. In addition, ocular medical history will be summarized for the study eye by treatment group separately for each phase.

Concurrent procedure is defined as any procedure performed on or after the date of the first dose of study treatment. The number and percentage of patients with concomitant procedures in each system organ class and preferred term will be summarized by treatment group separately for each phase. In addition, ocular medical history will be summarized for the study eye by treatment group separately for each phase.

Medical histories and concomitant procedures will be coded using the MedDRA, version 21.0 or newer.

Prior medication is defined as any medication taken before the date of the first dose of study treatment. *Concomitant medication* is defined as any medication taken on or after the date of the first dose of study treatment. The World Health Organization (WHO) Drug Dictionary Enhanced will be used to classify prior and concomitant medications by therapeutic class and drug name.

The number and percentage of patients with prior medications will be summarized under each drug class and drug name by treatment group separately for each phase. A separate summary for prior ocular medications used in the study eye under each drug name by treatment group separately for each phase. If a patient took a specific medication multiple times or took multiple medications within a specific therapeutic class, that patient would be counted only once for the coded drug name or therapeutic class. Formulations (including salts, esters, etc.) containing the same active ingredient will be pooled under the coded drug name of the base compound. Medications containing multiple active ingredients of different coded drug names will be reviewed during the course of the study and may be pooled under a single coded drug name for analyses.

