Similarly, the number and percentage of patients with concomitant medications will be summarized under each drug class and drug name by treatment group separately for each phase separately for Core Study Visits and Long-term Follow-up Visits. A separate summary for concomitant ocular medications used by eye (study eye and fellow eye) under each drug name by treatment group separately for each phase separately for Core Study Visits and Long-term Follow-up Visits.

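### SAP 15.9.1 and 15.9.2 resolve a start-after-stop conflict in opposite ways, and in one date pattern the apparent order counts a medication that ended before dosing as concomitant.

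*SAP*

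**What the plan says.** SAP 8.0 sorts medications by date. Prior means taken before the first dose. Concomitant "is defined as any medication taken on or after the date of the first dose of study treatment". The outputs include prior and concomitant tables by dose group and phase, and "A separate summary for concomitant ocular medications used by eye (study eye and fellow eye) under each drug name by treatment group".

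SAP 15.9 completes partial dates. On order it says: "When the start date and the stop date are both incomplete for a patient, the start date will be imputed first".

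SAP 15.9.1, start dates. If month and day are missing and the year is the dosing year, "the month and day of the first dose of study treatment will be assigned to the missing fields". An earlier year becomes 31 December of that year. On conflict, for a stop that is complete "or imputed) and the imputed start date is after the stop date, the start date will be imputed using the stop date".

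SAP 15.9.2, stop dates. If only the day is missing and the month precedes the dose month, "the last day of the month will be assigned to the missing day". On conflict, where an "imputed stop date is before the start date (imputed or non-imputed start date), the imputed stop date will be equal to the start date".

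Each patient receives one injection (SAP 9.2), so first and last dose dates coincide in these rules.

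**The concern.** For a pair in which both dates are imputed and the start lands after the stop, the two conflict sentences give opposite answers. The SAP does not say which governs. The only guide is the order of imputation: no imputed stop exists yet when 15.9.1 is worked through, so 15.9.2 naturally acts last and its answer stands.

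That answer can replace recorded information with a guess. A start known only by year is placed on the dose date by convention. A stop recorded to the month is a fact about when the course ended. Under 15.9.2 the convention overrides the fact, and a course that ended before the injection is shown as taken on the day of injection. A pre-entry eye drop could then appear in the by-eye concomitant table for that dose group and be absent from the prior table. Recording the stop date more precisely reverses the result, which an imputation rule should not allow.

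**Working it through.** The plan gives no figure to reproduce, so the check codes the rules and follows the dates. The documents give no real dates; a dose date of 15 June 2018 is assumed.

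**Inputs.** Order of imputation: SAP 15.9. Start rules and conflict rule: 15.9.1. Stop rules and conflict rule: 15.9.2. Classification: SAP 8.0.

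**Step 1, the failing case.** Start recorded as 2018, stop as March 2018.

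| Stage | Start | Stop | Class |
|---|---|---|---|
| After imputation | 15 Jun 2018 | 31 Mar 2018 | conflict |
| 15.9.2 applied | 15 Jun 2018 | 15 Jun 2018 | concomitant, not prior |
| 15.9.1 applied | 31 Mar 2018 | 31 Mar 2018 | prior, not concomitant |

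With the stop recorded in full as 10 March 2018, 15.9.2 does not act, because it concerns imputed stops only. 15.9.1 sets the start to 10 March and the drug is prior.

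**Step 2, how far it reaches.** Start and stop can each be complete, month-and-year or year-only: nine combinations. Take courses whose recorded stop shows that they ended before dosing, and apply the stated order. Only a year-only start with a month-and-year stop produces errors, and only when the start year is the dosing year. Within that pattern every record is wrong.

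Now count date combinations with both dates partial, the stop month known and before the dose month, and years 2016 to 2018. For the June dose date:
- start month missing, start in the dosing year: 5 combinations, all concomitant only;
- start day missing, start in the dosing year: 15, all prior;
- start month missing, start in an earlier year: 46, all prior;
- start day missing, start in an earlier year: 420, all prior.

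So 5 change and 15 + 46 + 420 = 481 do not. In general a dose in month m has m − 1 affected stop months: 0 for January, 11 for December. These are counts of date patterns, not expected patient frequencies.

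**Step 3, effect on a table cell.** One affected patient moves a drug row by 1/3 = 33 percentage points in a Phase 1 group of 3. In Phase 2a the shift is 1/12 = 8 to 1/6 = 17 points.

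**Step 4, testing the remedy.** The broad remedy moves the start back whenever the start was imputed. It clears Step 2 but fails elsewhere. Start September 2020 with stop 2020 imputes to 1 September and 1 January 2020, and the broad remedy sets both to 1 January 2020. Month 24 falls in June 2020, so the drug moves from long-term follow-up into the core period, and SAP 8.0 tabulates these separately. Take month-and-year starts after the dose month, 2018 to 2023, with a year-only stop in the same year: 6 + 5 × 12 = 66 patterns. The broad remedy pulls the start out of its recorded month in 6 + 5 × 11 = 61. The current 15.9.2 does so in none.

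A rule keyed to a missing start month gives 0 errors in the nine-combination check and 0 of 66 here.

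**The case against.** The strongest reply is that 15.9 orders the imputation, not the resolution of conflicts. 15.9.1 expressly covers an imputed stop. With the start imputed first, those words do nothing for two partial dates unless the 15.9.1 check is repeated once the stop is known, and repeating it gives the right answer. This stands in part: the SAP does not establish that patients would be miscounted. It does establish that two programmers following the text could reach different tables.

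A reader might infer that any record with two partial dates is misclassified. The text does not support that. The failure needs a start with the month missing and a start year equal to the dosing year; Step 2 shows all other patterns staying prior.

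A reader might also infer that 15.9.1 should simply prevail. Step 4 argues against it: read literally, 15.9.1 carries the same hazard as the broad remedy, and 15.9.2 protects recorded start months.

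Frequency is also open. Protocol 5.2.2 records current medication use and screening reaches back at most 45 days, so a drug stopped in March might never be recorded for a June dose. But Protocol 5.2.3 asks for all medications, SAP 8.0 sets no look-back limit for prior medication, and a drug stopped in May would fall inside that screening window.

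Finally, steroid examples are narrowed by the exclusions for immunosuppressive medication and for recent study-eye injections. That is fair, although topical drops are not listed there.

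**Conclusion.** The concern holds in a narrow form. The two conflict rules contradict each other, and the order in 15.9 favours the one that can override a recorded stop month. The wrong result is confined to a start known only as the dosing year with a stop in an earlier month of that year.

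The consequence is minor. Only descriptive prior and concomitant medication tables are touched; no primary safety endpoint, escalation decision or test depends on them. The 33 points is an upper limit for one drug row in a group of 3. SAP 8.0 counts a patient once per drug name or class, so the shift is zero if that patient has another qualifying record in the row.

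The conclusion rests on two assumptions: that 15.9.2 is applied after 15.9.1 without rechecking, and that such records are collected at all. The 15 June 2018 date only illustrates; the pattern is the same for every dosing month from February on.

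**What to change.** Replace the conflict sentence in SAP 15.9.2 with a rule on these lines: *Where the imputed stop would precede the start and the month of the start was not recorded, set the start to the imputed stop. In every other such case, set the imputed stop to the start.* In 15.9.1, delete the reference to an imputed stop or make it follow the same rule, so that one rule governs each conflict.

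Do not extend the first half to every imputed start, for the reason in Step 4.

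At the same edit, correct the cross-reference in 15.9.2: it points to Section 15.4 for a missing last-dose date, but that rule is in Section 15.5.

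The cost is a small edit to two SAP sections and a matching condition in the date-imputation code. Nothing changes in data collection or for patients, and it can be done at any time before database lock.

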15.10 CHARACTER VALUES OF CLINICAL LABORATORY PARAMETERS

If the reported value of a clinical laboratory parameter cannot be used in a statistical summary table because, for example, a character string is reported for a parameter of the numeric type, a coded value must be appropriately determined for use in the statistical analyses. The actual values, however, as reported in the database will be presented in the data listings.

Error! Reference source not found. shows examples of how some possible laboratory results should be coded for the analysis.

Table 15.10–1. Examples of Coding Special Character Values for Clinical Laboratory Parameters

Laboratory Test	Possible Laboratory Results (in SI Units)	Coded Value for Analysis
Chemistry: ALT	< 5	5
Chemistry: AST	< 5	5
Chemistry: bilirubin, total	< 2	2

ALT = alanine aminotransferase; AST = aspartate aminotransferase; SI = *Le Système International d'Unités* (International System of Units).

16.0 CHANGES TO ANALYSES SPECIFIED IN PROTOCOL

There are no changes to the analyses specified in the protocol Amendment 2 (dated 19OCT2017).

